#### **10.3.2. Case Report Forms**

Copies of pertinent records relevant to the study, including all source documents, will be made available to the Sponsor or its designee on request with due precaution towards protecting the privacy of the patient.

Data will be entered by the site onto the eCRFs in the EDC system. Unless explicitly directed, blank data fields are not acceptable. Any erroneous entries made on the eCRFs should be corrected. Changes made to the data after initial entry into the eCRF will be captured via an electronic audit trail, and should include the reason for change. Incomplete entries or entries needing additional explanation will be highlighted or queried to the Investigator for clarification.

### **10.3.3. Record Retention**

The enrolling Investigator is responsible for oversight and maintenance of the study records and patient source documents unless the patient is transferred to another site for all subsequent visits. These records must be readily available for audit or inspection.

The Investigator must retain study records for at least 2 years after the last marketing approval has been granted, or at least 2 years have elapsed since the formal discontinuation of clinical program. However, these documents should be retained for a longer period, if required by other applicable requirements (e.g., applicable local regulatory requirement) or by an agreement with the Sponsor or its designee. The Investigator should contact the Sponsor or its designee prior to any record destruction.

Patient records or other source data must be kept for the maximum period of time mandated by the hospital, institution, or private practice, but not less than 15 years.

If off-site archiving is used, all records should be retrieved and made available for review at the time of an audit or regulatory authority inspection.

### **10.3.4. Monitoring**

A representative of the Sponsor or its designee will visit the Investigator periodically for the purpose of monitoring the progress of this study in accordance with the protocol, GCP, and local regulations. Noncompliance with the protocol, GCP, and local regulations will be documented and corrective actions implemented, as necessary. It is the responsibility of the Investigator to be present or available for consultation during monitoring visits. During these routine visits, all data pertaining to a patient's participation in this clinical investigation must be made available to the monitor.

Monitoring during the COVID-19 pandemic is subject to Investigator and/or local restrictions. It is possible that after local restrictions are lifted, monitoring may resume with more intense pace to clean all data accumulated during the pandemic.

At any time prior to, during, or after completion of the clinical study, an audit may be performed by the Sponsor or its designee or a representative of a national regulatory agency may choose to inspect a study site. Investigators should notify the Sponsor or its designee upon notification of inspection by a representative of a national regulatory agency. A Sponsor or designee representative will be available to assist in the preparation for study site inspections. All pertinent study data should be made available for verification, audit, or inspection purposes.

### **10.3.5. Study or Site Termination**

If the Sponsor, the Investigator, or regulatory authorities discover any conditions during the study that indicate that the study or study site should be terminated, this action may be taken after appropriate consultation between the Sponsor and the Investigator. The Sponsor has the right to terminate the participation of either an individual site or the study at any time, for any reason, which may include the following:

- The incidence and severity of AEs in this or other studies indicates a potential health hazard to patients
- Patient enrollment is unsatisfactory

- Data recording is inaccurate or incomplete.
- Investigator(s) does not adhere to the protocol or applicable regulatory guidelines in conducting this study
- Submission of knowingly false information from the study site to the Sponsor or regulatory authorities

In the event that the study is terminated early, the Sponsor will provide specific guidance to investigational sites regarding the end-of-study procedures.

### **10.3.6. Investigational Product Control**

#### **10.3.6.1. Receipt of Investigational Product**

A proof of receipt, which details the quantity and description of the investigational product, will accompany the shipment from the Sponsor or designee to the Investigator. The site must acknowledge each shipment of investigational product in the IWRS system once received. The Investigator must ensure that the investigational product is maintained in a controlled location, with limited access, and under adequate storage conditions (as described in [Section 5.1.4](#)).

#### **10.3.6.2. Disposition of Unused Investigational Product**

All unused investigational products must be maintained under adequate storage conditions in a limited-access area. If any unused material is remaining upon completion of the study, the material will be returned to the Sponsor or destroyed only after the following has been completed:

- Accountability has been performed by a representative of the Sponsor.
- Approval to return or destroy unused Investigational Product. Refer to the SDHM for further details.

#### **10.3.6.3. Product Handling and Complaints Reporting**

If there are any issues during the study related to the quality of the Investigational Product, the clinical site pharmacist or pharmacy designee should contact the Sponsor.

#### **10.3.7. Disclosure of Data**

All details related to the disclosure and publication of study data will be addressed in the Investigator's study contract.

#### **10.3.8. Confidentiality and Data Privacy**

Personal data recorded on all documents will be regarded as strictly confidential and will be handled and stored in accordance with the General Data Protection Regulation (GDPR 25May2018) in European Union Member States.

Sponsor affirms the patient's right to protection against invasion of privacy and to be in compliance with ICH and other local regulations (whichever is more stringent). Sponsor requires the Investigator to permit sponsor representatives (monitor) and when necessary, representatives from regulatory authorities, to review and/or copy any medical records relevant to the study in accordance with local laws (any copies of patients' records must be duly anonymised to protect patients' confidentiality).

Should direct access to medical records require a waiver or authorisation separate from the patient's statement of informed consent, it is the responsibility of the Investigator to obtain such permission in writing from the appropriate individual. Representative of the sponsor may be required to have access to patient's medical records for quality assurance purposes but patients should be reassured that their confidentiality will be respected at all times.

Representative of sponsor must maintain the confidentiality of all patient's data and will not disclose information by which patients may be identified to any third party other than those directly involved in the treatment and organization for which the patient has given explicit consent for data transfer.

**APPENDIX 1. SCHEDULE OF ASSESSMENTS**

Study Week(s)	Screen a	BL b	Double Blind, Placebo-Controlled Treatment (Weeks 1 - 52)								Safety F/U c
	-4 - 0	0	6	13	19	26	32	39	45	52/ET d	
Informed Consent/Assent	X										
Site Visit e	X	X		X		X		X		X	
Site Call e, f			X		X		X		X		X
Med History/Demographics	X										
Confirm Eligibility	X	X									
Randomization g		X									
Vital Signs	X	X		X		X		X		X	
Weight	X	X		X		X		X		X	
Height		X				X				X	
Physical Examination	X	X		X		X		X		X	
AEs/Con Meds h	X		Continuous								
12-Lead ECG i	X					X				X	
Cardiac Monitoring j	X					X				X	
Hematology/Chemistry k	X	X		X		X		X		X	
ACTH/Cortisol k		X		X		X		X		X	
Urinalysis	X					X				X	
DNA Sample l		X									
Biomarkers, Gene Expression k		X		X		X		X		X	
NSAA, Stand from Supine, 10MWT, 4-Stair Climb, Muscle Strength m	X	X		X		X		X		X	
PUL n		X				X				X	
Videotape Functional Assessments o	X	X								X	
PODCI p		X								X	
Lateral Spinal Radiography, DXA q		X								X	
Study Drug Questionnaire						X					
Nutritional Guidance r		X									
Drug Dispensation		X		X		X		X			
Drug Accountability				X		X		X		X	
PK (plasma and urine) s				X		X				X	

a Per Investigator's discretion, informed consent, medical history/demographic data and lab assessments may be completed remotely by a qualified medical professional.

b The first day of study drug is "Day 1"; unless otherwise specified, all assessments should be completed within a 4 week window prior to Day 1.

c Safety follow-up should occur within 2 wks. after last dose of study drug. Patients continuing in the open-label extension study are not required to perform the safety follow-up.

d If patient discontinues treatment early, patient will be asked to return for early termination (ET) visit prior to their last dose of study drug. Functional assessments performed within 6 weeks of discontinuing treatment do not need to be repeated at the ET visit. If the ET visit occurs after drug has been discontinued, certain assessments may be omitted per Sponsor discretion.

- e Weeks 6-19 should be conducted within the study week with a  $\pm 4$ -day window. Weeks 26-54 have a  $\pm 10$ -day window.
- f Per Investigator discretion, site calls may occur by telephone or use of other technology.
- g Randomization occurs after Screening assessments have been completed and eligibility is confirmed.
- h AEs and concomitant medication/therapy will be assessed at all visits and during site calls.
- i ECGs will be performed predose at all timepoints. At Week 26, ECG will be performed predose and 2 hours postdose ( $\pm 15$  min).
- j Cardiac monitoring will be performed for approximately 48 hours remotely via a wearable cardiac monitoring device if approved for use in the participating country.
- k Blood samples will be drawn in the morning when possible.
- l DNA sample may be collected at Baseline for drug metabolizing enzyme and/or transporter analysis as well as pharmacogenomic analysis of potential markers of clinical risk/benefit.
- m Assessments should be performed in the order listed and in the morning when possible. Time to stand from supine and 10MWT will be recorded as measured in the NSAA.
- n The PUL 6-point entry item scale will be performed at all timepoints. If a patient scores a 6 on the PUL entry item scale, no further PUL testing is required for the visit.
- o Videotaping at Baseline is required if Screening video did not pass QC.
- p PODCI will be performed when feasible.
- q These assessments should be collected within 2 months prior to Day 1. In Germany, bone assessment will not be performed until the respective approvals from the German Federal Office for Radiation Protection (Bundesamt für Strahlenschutz) become available.
- r Patient compliance with the nutritional guidance will be confirmed throughout the trial.
- s Urine PK collection will be performed at Week 13. Plasma PK collection will be performed predose at Week 13 and Week 52. At Week 26 plasma PK collection will be performed predose, 1 hour ( $\pm 5$  min), 2 hours ( $\pm 15$  min), and 4 hours ( $\pm 15$  min) postdose.

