3. PATIENT POPULATIONS

3.1. Population Definitions

The following patient populations will be evaluated and used for presentation and analysis of the data:

- Randomized Population: all patients who are randomized into the study with patients to be analyzed based on the study treatment they were randomized to.
- Safety Population: all patients who receive at least one dose of study drug with patients to be analyzed based on the actual study treatment received.
- Full Analysis Population (FAP): all patients in the Randomized Population who receive at least one dose of study drug and provide at least one non-missing post-Baseline NSAA efficacy assessment.
 - Note that the FAP will exclude patients on eteplirsen at randomization and patients will be analyzed based on the study treatment they were randomized to.
- Per Protocol (PP) Population: all patients in the FAP who complete the 52-week treatment period of the study without any significant protocol deviations with patients to be analyzed based on the study treatment they were randomized to.

The set of patients in the Per Protocol population may be updated due to study drug compliance information which will not be collected until after database lock and unblinding due to the COVID-19 pandemic, see [Section 3.2](#).

note: the variable to determine a patient completing the 52-week treatment period is from the End of Study eCRF page “Did subject complete the study?” = Yes.

The FAP will be the primary population for the analysis of efficacy parameters. The Safety Population is the primary population for the analysis of safety endpoints.

Note that if siblings are enrolled, only one sibling will be included in the Randomized Population. This is to avoid having siblings being randomized to different study medications, increasing the risk a subject will inadvertently take incorrect study medication. The second sibling will be assigned to the same treatment group as the randomized sibling. If both siblings meet the inclusion/exclusion criteria, the sibling to be included in the Randomized Population will be the first sibling randomized, both siblings will be included in the Safety Population (see [Section 3.1](#)). The sibling not included in the Randomized Population will have their data presented in the listings and will be included in some of the sensitivity analyses.

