4.2.11. Baseline

A patient’s baseline value will be most recent non-missing value occurring prior to initiation of study drug. In most cases this will be the value assessed at the Baseline visit. If the Baseline value is missing, the next most recent non-missing value will be used (i.e., in most cases this will be the Screening visit value).

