4.10.4. Sensitivity Analyses for the Primary Efficacy Endpoint

The following sensitivity analyses of the primary and secondary efficacy endpoints will be performed to assess the robustness of the analyses across endpoints:

a) The primary efficacy endpoint analysis performed on the PP population

The primary efficacy endpoint analysis, as defined in [Section 4.10.1](#) will be performed using the PP Population

b) The primary efficacy endpoint analysis performed on the Randomized population

The primary efficacy endpoint analysis, as defined in [Section 4.10.1](#) will be performed using the Randomized Population (note: this includes randomized patients on eteplirsen)

c) ANCOVA on the primary efficacy endpoint using MAR, MNAR, and OC

The primary efficacy endpoint, the CFB in the NSAA Total Score at Week 52 will be analyzed by an ANCOVA model. The ANCOVA model will include CFB in the NSAA Total Score at Week 52 as the dependent variable, treatment and region (North America vs. Europe/Asia/Australia) as factors, and baseline age (as a continuous variable), baseline time

to stand from supine (as a continuous variable), and baseline NSAA score (as a continuous variable) as covariates.

Three different methods of addressing missing data will be performed:

- 1) **Missing at Random (MAR)** Missing data will be imputed using the MAR algorithm described in [Section 4.10.6.1](#).
- 2) **Missing Not at Random (MNAR)** Missing data will be imputed using the MNAR algorithm described in [Section 4.10.6.2](#).
- 3) **OC (Observed Case)** this ANCOVA will be performed on non-missing data.

These analyses will be performed on the FAP.

d) Observed Week 52 MMRM

The primary efficacy endpoint analysis will be repeated (i.e., as described in [Section 4.10.1](#)) subset to those patients who had a non-missing CFB value at Week 52.

e) MMRM with multiple imputation assuming MAR

The primary efficacy endpoint analysis will be repeated (i.e., as described in [4.10.1](#)) with missing data imputed based on a Missing at Random (MAR) pattern as described in [4.10.6.1](#).

f) MMRM with multiple imputation assuming MNAR

The primary efficacy endpoint analysis will be repeated (i.e., as described in [4.10.1](#)) with missing data imputed based on a Missing Not at Random (MNAR) pattern as described in [4.10.6.2](#)

g) Including siblings

The primary efficacy endpoint analysis will be repeated (i.e., as described in [4.10.1](#)) including the siblings in the FAP.

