4.10.6.2. MMRM with Multiple Imputation Assuming MNAR

Imputation algorithm:

For this imputation the monotonic missing post-baseline change from baseline scores will be imputed via multiple imputation assuming MNAR for each scheduled assessment visit (i.e., Weeks 13, 26, 39, and 52).

The imputation of monotonic missing scores in the edasalonexent treatment group will be based on the distribution in the placebo group. This method assumes that the trajectory of withdrawals from the edasalonexent treatment arm follows the distribution of the placebo patients. The MNAR option in Proc MI (SAS system) will be used to impute the placebo distribution as described (Yuan, 2014).

Fifty imputed datasets will be created. Each of the imputed datasets will be analyzed via the same model as the primary efficacy endpoint analysis (see Section 4.10.1). The results across the multiple imputed data sets will be combined using SAS Proc MIANALZYE (details provided in APPENDIX 2: Sample Multiple Imputation Code).

The set of variables for this MNAR multiple imputation model is the same set as defined for the MAR multiple imputation (Section 4.10.6.1), with the exception of Treatment group, which is not included in the MNAR imputation (i.e., the placebo distribution is used to impute the data).

The imputations will be performed using monotone linear regression imputation methods which will impute the patients' missing post-baseline change scores at each of the scheduled visits in the study (i.e., Weeks 13, 26, 39, and 52).

If the missing data does not follow a monotonic pattern, a sequential approach to imputing the data via an MCMC method to produce a monotone missing data pattern will be applied using the MCMC impute=monotone option in Proc MI (SAS System). Following the method described in Smith (2017) the non-monotonic data imputation will be performed "by" the categorical treatment variable (note: the categorical variable Region will not be included in the non-monotonic imputation). Then the monotone linear regression imputation methods will be applied.

Note: if the multiple imputation model does not converge or produce estimates (i.e., due to over-specification) the set of imputation variables may be modified.

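### Boys who stop soon after Baseline and are never retested fall outside the planned imputation analyses; widening the imputation population would close this small gap

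*Protocol*

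**What the plan says.** **Waiver.** Both schedules carry the same sentence in footnote d: "Functional assessments performed within 6 weeks of discontinuing treatment do not need to be repeated at the ET visit". Neither says that the earlier test must be post-Baseline.

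**Testing schedule.** The row headed "NSAA, Stand from Supine, 10MWT, 4-Stair Climb, Muscle Strength" in Protocol Appendix 1 is marked at Screening, Baseline, Weeks 13, 26 and 39, and Week 52/ET. Footnote b adds that, unless otherwise specified, "all assessments should be completed within a 4 week window prior to Day 1". SAP 4.2.11 defines the baseline value as the "most recent non-missing value occurring prior to initiation of study drug".

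**Populations.** To enter the FAP under SAP 3.1, a randomised, dosed boy not on eteplirsen at randomisation must also "provide at least one non-missing post-Baseline NSAA efficacy assessment". The same section states: "The FAP will be the primary population for the analysis of efficacy parameters".

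**Analyses.** The primary MMRM (SAP 4.10.1) uses observed cases without imputation. In SAP 4.10.4:
- (c) is an ANCOVA under MAR imputation, MNAR imputation and observed cases, with the note "These analyses will be performed on the FAP".
- (e) and (f) repeat the primary analysis with MAR and MNAR imputation and name no wider population.
- (b) repeats the observed-case MMRM on the Randomized Population.
- (a) uses the Per Protocol subset of the FAP, (d) keeps only boys with a Week 52 value, and (g) adds siblings.

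On the MNAR imputation, SAP 4.10.6.2 says: "This method assumes that the trajectory of withdrawals from the edasalonexent treatment arm follows the distribution of the placebo patients".

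**The concern.** For a boy who stops within 6 weeks of his Baseline test, the only functional test inside the waiver window is a pre-dose one. The footnote allows the site to skip the exit NSAA, although SAP Table 4 would map an ET test from Day 2 onwards to Week 13 and use it. If he is not tested again, he has a baseline value and nothing else. A boy who misses the ET visit and is not seen again is in the same position.

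His absence follows from what happened after randomisation, which may differ by arm. The analyses meant to show how far dropout could change the result are confined to boys who pass this filter. The placebo-based imputation is described as covering withdrawals from the active arm, but it does not reach the earliest of them if they were never retested. Their contribution to that stress test is nil, whatever their number.

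**Working it through.** **Step 1: the path through the documents.** Take a boy tested at Baseline on Day 1 who stops on Day 30.

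| Situation | Post-Baseline NSAA? | In FAP? | Covered by imputation? |
|---|---|---|---|
| Exit test done at ET visit | Yes, mapped to Week 13 | Yes | Yes, for later visits |
| Exit test waived; stays in study and is tested at Week 13 | Yes | Yes | Yes; the post-stop value is censored (SAP 4.10) and can then be imputed |
| Exit test waived; not tested later | No | No | No |
| ET visit missed; not tested later | No | No | No |

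The last two rows are the gap. Those boys belong to the Randomized Population, but analysis (b) has no imputation, so they supply no outcome to it.

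**Step 2: length of the waiver window.** The 6 weeks run back from the stopping date to the test. With the Baseline test on Day 1, the window covers about 6 weeks on drug. With that test 4 weeks earlier, as footnote b allows, it covers 6 − 4 = 2 weeks.

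**Step 3: the plan's own figures (SAP 4.1).** 126 boys at 2:1 gives 84 active and 42 placebo. The difference is 3.0 and the SD 4.8, so 3.0/4.8 = 0.625, as stated. With 20% dropout, 126 × 0.8 = 100.8 boys remain (67.2 and 33.6). The standard error of the difference is 4.8 × √(1/67.2 + 1/33.6) = 1.01 points. Power at two-sided 0.05 is 84.1% (normal) or 83.4% (noncentral t), against the stated figure of approximately 80%. The stated figure is not reproduced exactly and is on the cautious side. The point here does not depend on it.

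**Step 4: boys exposed to the waiver.** The documents give no dropout timing, so every row is an assumption.

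| Assumed timing | Share stopping in window | Of 126 | Of 84 active |
|---|---|---|---|
| Constant hazard to 20% at Week 52, 2-week window: 1 − 0.8^(2/52) | 0.85% | 1.1 | 0.7 |
| Constant hazard, 6-week window: 1 − 0.8^(6/52) | 2.5% | 3.2 | 2.1 |
| A quarter of dropouts in the window: 0.25 × 20% | 5% | 6.3 | 4.2 |
| Half of dropouts in the window: 0.5 × 20% | 10% | 12.6 | 8.4 |

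These are boys exposed to the gap. Those tested at the ET visit or at Week 13 are not lost. Boys lost only because they missed the ET visit are not counted.

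**Step 5: effect on a placebo-based estimate.** Suppose k omitted active boys would have fared like placebo and the other active boys keep the assumed 3.0 points. The difference then falls by 3.0 × k/84:
- k = 2: 0.07 points
- k = 4: 0.14 points
- k = 8: 0.29 points

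Using the shares in Step 4, 3.0 × (1 − share) gives 2.92, 2.85 and 2.70 points for 2.5%, 5% and 10%. At a fixed 100.8 boys, normal-approximation power for those differences is 82.2%, 80.2% and 75.9%, against 84.1% at 3.0.

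Under MAR, boys with only baseline data are imputed from their own arm's model, so adding them should move the estimate little. The gain is mainly in the MNAR analyses.

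**The case against.** A reader might infer that every boy who stops in the first 6 weeks disappears from every efficacy analysis because of the waiver. The documents do not support this:

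- The footnote permits omission and does not require it. NSAA is marked in the 52/ET column, and boys who stop early are asked to attend the ET visit.
- Stopping drug is not leaving the study (Protocol 5.2.5). The SAP's FAP rule does not require the post-Baseline NSAA to be on treatment, so a boy tested at Week 13 enters and can be imputed.
- The waiver is not the only cause. The FAP entry rule, an openly declared modified intent-to-treat definition, and the restriction of imputation to the FAP would also drop a boy who misses the ET visit.

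Nor do the documents show that early stops would fall mainly on active drug. Protocol 2.2 reports gastrointestinal events as the most common, but mainly mild and transient, and Protocol 2.2 and 2.3 report no treatment-related discontinuations. These data are limited: no events among the 32 boys treated by June 2018 would still allow a true rate up to 1 − 0.05^(1/32), about 9% (one-sided 95% bound). An imbalance is a possibility, not a finding.

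The size is also small. A shift of 0.07 is well below the standard error of 1.01. The 8-boy case puts nearly half of the active arm's expected dropouts (84 × 0.2 = 16.8) into the first 6/52 = 12% of treatment, which nothing in the documents suggests.

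All of this stands. What remains is that boys never retested are outside the analyses designed to test dropout.

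**Conclusion.** The gap is real but narrow, and closing it is a cheap improvement. It concerns boys who have no NSAA after Baseline, whether because the exit test was waived or because the ET visit was missed. They are outside the FAP and outside the MAR and MNAR imputation analyses, and they add nothing to the observed-case analysis of the Randomized Population.

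About 3 of 126 boys are exposed through the waiver under a constant hazard, with a range of about 1 to 13 across the assumed timings. The effect on a placebo-based estimate is about 0.07 points for 2 active boys and 0.29 for 8. These figures rest on assumed dropout timing, on the SAP's 3.0-point difference, and on omitted active boys faring like placebo. The primary analysis is not invalidated. If no boy is in this position, the change alters nothing.

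**What to change.** **Main change (SAP 4.10.4 c(1), c(2), e and f, and by SAP 4.10.5 the secondary endpoints).** Run the multiple imputation on all randomised, dosed boys not on eteplirsen, including those with no post-Baseline NSAA. Impute their Week 13 to 52 changes from the baseline variables already in the model: region, age, time to stand and baseline score, plus treatment under MAR. A boy missing all four visits fits the planned monotone scheme. Keep the FAP for the primary MMRM, and report by arm how many boys are added.

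This needs no new data and should be settled before unblinding. The cost is a wording change, a small addition to the programming, and a placebo-based estimate that may be slightly less favourable.

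**Secondary change (footnote d in Protocol Appendix 1 and SAP Table 1).** Limit the waiver to functional assessments done after Baseline. Protocol Appendix 2 says enrolled patients had already completed at least Week 26 when the pandemic began, so this would collect little or nothing here. It is useful mainly if the schedule is used again, at the cost of one functional test session for each boy affected, at a visit he is already asked to attend. It does not replace the main change, because a boy who misses the ET visit would still be left out.
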